Comparative pharmacokinetic (PK) analysis between ADVL1414 and multiple adult studies suggest Cmax and AUC values at 20 mg/m^2 were similar to those seen at 35 mg/m^2 dosing in adults, and values at 35 mg/m^2 compared favorably to those seen at doses up to 60 mg/m^2 in adults. 35 mg/m^2 dosing in children would therefore appear to produce at least equivalent PK values to the 80 mg flat dosing that produced the best responses in the KING trial, even when given weekly. A dose of 20 mg/m^2, on the other hand, is unlikely to produce adequate exposure for CNS tumor response, based on available clinical and preclinical data. Since progress in the trial to this point has demonstrated 20 mg/m^2 twice weekly (40 mg/m^2 cumulative per week) to be tolerable, we will use 45 mg/m^2 (a 12.5% increase in dose intensity) as our starting dose on the once weekly schedule which is anticipated to be less toxic than twice weekly dosing. We will have one dose escalation to 55 mg/m^2 and one available de-escalation to 35 mg/m^2, the lowest dose considered likely to produce adequate CNS exposure to be efficacious based on available evidence. We hypothesize that tolerability will be improved, that the RP2D for weekly dosing will be higher than the current RP2D for twice weekly dosing, and that Cmax and AUC values equivalent or higher will be achieved and compare favorably to the dosing levels in adults at which responses have been observed.

Table A:

		Dose (mg/m  )	T max (hr)	C max (ng/ml)	t 1/2 (hrs)	AUC (hr*ng/ml)	C 1/F (L/hr/m  )
ADVL1414	Solid Tumors; Tablet with food Schedule- Days 1, 3, 8, 10, 15, 17, [22, 24]; PK- T= 0, 0.5, 1, 3, 4, 6, 8, 24 h	35, (n=19)	2 (0.5-6)	535 ± 174	7.9 ± 4.1	5156 ± 1227	7.12 ± 1.34
		20 (n=12)	4 (1-6)	324 ± 116	7.2 ± 1.2	3092 ± 842	6.98 ± 1.55
Alexander et al, 2016	Pediatric Acute Leukemia, No acetaminophen; Schedule- Days 1, 3, 8, 10, 22, and 24. PK- T=0, 0.5, 1, 2, 4, 8, 24, 48 h	30 + fludarabine (n=4)	3 ± 1.5	537 ± 281	6 ± 1	AUC 0-48h = 4,351 ± 513	
Abdul Razak et al, 2016	Adult Solid Tumors Schedules- Multiple; PK- T= 0, 0.5, 1, 2, 4, 8, 24, 48 h	20 (n=5)	4 ± 3	237 ± 105	6 ± 1	AUC 0-48h = 2,614 ± 603	
		35 (n=10)	4 ± 2	358 ± 82	7 ± 4	AUC 0-48h = 3,901 ± 932	

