## 4.1 Inclusion Criteria

- 4.1.1 Age: Patients must be  $\geq$  than 12 months and  $\leq$  21 years of age at the time of study enrollment.
- 4.1.2 BSA: Patients must have a BSA  $\geq$  0.84 m^2.
- 4.1.3 Diagnosis:
- 4.1.3.1 Part A: Patients with recurrent or refractory solid tumors, including lymphoma and CNS tumors, are eligible. Patients must have had histologic verification of malignancy at original diagnosis or relapse except in patients with intrinsic brain stem tumors, optic pathway gliomas, or patients with pineal tumors and elevations of CSF or serum tumor markers including alpha-fetoprotein or beta-HCG.
- 4.1.3.2 Part B: Patients with recurrent or refractory high grade glioma (WHO Grade III/IV) including disseminated tumors (excluding DIPG), not requiring surgical resection. Patients must have had histologic verification of malignancy at original diagnosis or relapse.
- 4.1.3.3 Part C: Patients with recurrent or refractory high grade glioma (WHO Grade III/IV) and requiring surgical resection (excluding DIPG and disseminated tumors), who in the opinion of treating physicians, are medically stable to receive 2 doses of selinexor (8-10 days of treatment) before undergoing surgery without compromising the success of the procedure. Note that if, in the opinion of treating physicians, current symptoms necessitate surgery before 2 doses will be able to be received, surgery should not be delayed to administer selinexor, and the patient would be ineligible for protocol therapy.
- 4.1.4 Disease Status:
- Part A: Patients must have either measurable or evaluable disease (see Sections [12.2](#) and [12.3](#) for definitions).
- Parts B & C: Patients must have measurable disease on imaging.
- 4.1.5 Therapeutic Options: Patient's current disease state must be one for which there is no known curative therapy or therapy proven to prolong survival with an acceptable quality of life.
- 4.1.6 Performance Level: Karnofsky  $\geq$  50% for patients  $>$  16 years of age and Lansky  $\geq$  50 for patients  $\leq$  16 years of age (See [Appendix I](#)). Note: Neurologic deficits in patients with CNS tumors must have been relatively stable for at least 7 days prior to study enrollment. Patients who are unable to walk because of paralysis, but who are up in a wheelchair, will be considered ambulatory for the purpose of assessing the performance score.
- 4.1.7 Prior Therapy

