5.3.2 Part B: Non-Surgical HGG Expansion Cohort

Patients with HGG not requiring resection will be treated at the recommended phase 2 dose (RP2D) determined from the phase 1 component (Part A) of this trial.

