However, a dose level will be repeated with required maximal antiemetic therapy (5-HT3 antagonists and another antiemetic) prior to each dose during Cycles 1 and 2 if DLTs of vomiting or dehydration is experienced in  $\geq 2/6$  evaluable patients at a dose level. This condition would increase the expected maximum to 38 which allows for 12 patients at one dose level, 6 at the two other dose levels, 6 PK, and 20% inevaluability. This would be expected to be completed within 19-38 months.

In the unlikely event that all dose levels required expansion to 12 patients per [Section 11.2.2](#), then the absolute maximum would be 68 patients. This includes 24 patients at a single dose level requiring expansion due to both 1) toxicities of different classes and 2) DLTs of vomiting or dehydration as well as 12 patients at each of the other two dose levels, 6 PK, and 20% inevaluability. This would be expected to be completed within 34-68 months.

The study has currently enrolled 31 patients (Fall 2019 SPR).

Non-Surgical Cohort (Part B): 10 evaluable patients with recurrent/progressive HGG (excluding DIPG) who do not require resection will be enrolled in a medical dose-expansion cohort (Part B) and will be treated at the MTD on the same schedule. If at any time greater than one out of three patients (or 33%) of the cohort of patients experience DLT, the cohort will be closed to further accrual. All patients enrolled on Part A who meet the eligibility criteria for Part B of the study who are evaluable for response as outlined in [Section 11.2.3](#) of this protocol will be included in the evaluation rule.

Surgical Cohort (Part C): Up to 10 evaluable patients with recurrent/progressive HGG (excluding DIPG and disseminated tumors) for whom resection is recommended by their treating teams will be enrolled in a surgical dose-expansion cohort. These patients will be allowed to receive up to four doses of selinexor prior to resection. After their resection and when medically cleared, they will restart selinexor on the prior schedule. The purpose of this cohort will be to perform pharmacokinetic and pharmacodynamic studies on the tumor tissue, and to explore preliminarily the effectiveness of selinexor in this disease. If at any time greater than one out of three patients (or 33%) of the cohort of patients experience DLT, the cohort will be closed to further accrual.

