Accrual to Parts B and C will only open once the MTD or recommended phase 2 dose has been determined in Part A, and may open concurrently with the PK expansion described above.

A maximum of 24 patients are expected to enroll in Parts B and C combined, assuming an inevaluability rate of 20%. We anticipate that each part of the study will require 6-12 months for enrollment.

Response for Part B will be defined as either MR, PR or CR on two consecutive 2D measurements on standard imaging done 4 weeks apart (See [Section 12.6](#)). Sustained responses are very rare in this cohort of recurrent non-DIPG HGGs. We will consider the agent of sufficient interest for further evaluation in this disease category if at least one PR or CR, or at least two MRs, is observed among 10 enrolled patients. A response rate of 20% or more would be evidence of sufficient activity. If the true response rate is 20%, then the probability of observing one or more responses among 10 evaluable patients is about 89.3%. If the response rate is 5%, then the probability of observing at least one response is about 40.1%.

Clinical benefit for Part C will be evaluated separately using the criteria of no visible disease progression six months from the start of treatment. If two or more of a cohort of up to six patients are unable to resume therapy within 6 weeks after surgery, the surgical arm will be declared not feasible. If Part B has fully accrued, Part C will close to further accrual.

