### 11.2.3 Evaluability for Response

Any patient who is enrolled who meets eligibility criteria for Part B and receives at least one dose of selinexor will be considered evaluable for response provided: (1) the patient demonstrates progressive disease or death while on protocol therapy; or (2) the patient is observed on protocol therapy for at least one cycle and the tumor is not removed surgically prior to the time complete response or partial response is confirmed, or (3) the patient demonstrates a complete or partial response as confirmed according to protocol criteria. Patients who demonstrate a complete or partial response confirmed by central review will be considered to have experienced a response for the application of the rule given in [Section 11.1](#). All other patients will be considered non-responders. All patients considered to have a response (CR, PR, or MR) must have imaging studies reviewed centrally at the COG. Centers will be notified by the COG about requests for scans of patients with stable disease. See [Section 8.2](#) regarding image submission instructions. The central review by COG will be provided as the final reviewed assessment of response when such becomes available.

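### The Part B activity rule counts Part-B-eligible Part A patients from any dose level or schedule and does not fix the denominator, so the stated probabilities need not describe the rule as applied

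*Combined protocol and SAP*

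**What the plan says.** Part B is the non-surgical high-grade glioma (HGG) expansion. Section 5.3.2 sets its dose: "Patients with HGG not requiring resection will be treated at the recommended phase 2 dose (RP2D) determined from the phase 1 component". Section 11.1 adds that the cohort is treated at the MTD on the same schedule, which under Amendment #4 is once weekly.

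Section 11.1 then widens the group to which the rule applies. It includes "All patients enrolled on Part A who meet the eligibility criteria for Part B of the study who are evaluable for response" as Section 11.2.3 defines it. That section reads: "Any patient who is enrolled who meets eligibility criteria for Part B and receives at least one dose of selinexor will be considered evaluable", subject to progression or death on therapy, one cycle of observation, or a confirmed response. It also ties the definition to the decision: a centrally confirmed CR or PR "will be considered to have experienced a response for the application of the rule given in" Section 11.1.

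The rule in Section 11.1 is met "if at least one PR or CR, or at least two MRs, is observed among 10 enrolled patients". Section 11.1 gives the probability of at least one response among 10 evaluable patients as about 89.3% if the true rate is 20% and about 40.1% if it is 5%.

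Part B eligibility in Section 4.1 concerns disease, not regimen: "Patients with recurrent or refractory high grade glioma (WHO Grade III/IV) including disseminated tumors (excluding DIPG), not requiring surgical resection", with measurable disease. Part A is open to such patients: "Patients with recurrent or refractory solid tumors, including lymphoma and CNS tumors, are eligible".

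**The concern.** The cohort that Part B treats and the cohort that the rule counts are not the same. Part B patients receive one dose on one schedule. The Part A patients who join them may have been treated twice weekly for 8 doses per cycle, twice weekly for 6 doses with a rest week, or once weekly at 35, 45 or 55 mg/m2. Of the 20 mg/m2 dose, Section 2.8 says that it "is unlikely to produce adequate exposure for CNS tumor response", yet a patient treated at that dose would count the same as one treated at the RP2D.

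This matters because one PR or CR is enough to meet the rule. A response on a replaced regimen could meet it with no responder at the RP2D. Conversely, if Part A patients occupy some of the 10 places, non-responders at a dose the protocol considers too low leave fewer RP2D patients in whom a response could be seen. The text does not settle which situation applies, so the probabilities in Section 11.1 cannot be attached to the rule with confidence.

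**Working it through.** **Inputs.** From Section 11.1: 10 patients, true rates of 20% and 5%, 31 patients enrolled by Fall 2019. From Table A in Section 2.8: 19 patients of this trial with pharmacokinetic data at 35 mg/m2 and 12 at 20 mg/m2, on the twice-weekly schedules. The number k of Part A patients who meet Part B eligibility and are response-evaluable is not given, so a range is assumed.

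**Step 1: the plan's own figures.** P(at least one response) = 1 − (1 − p)^10.
- p = 0.20: 1 − 0.80^10 = 0.893
- p = 0.05: 1 − 0.95^10 = 0.401

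Both figures reproduce, for exactly 10 patients sharing one rate.

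**Step 2: is k above zero plausible?** Part A admits CNS tumors. Table A's counts sum to 19 + 12 = 31, the same as the Fall 2019 enrollment. That is consistent with all patients enrolled by then having been on twice-weekly dosing, though the documents do not say that these are the same 31. Nowhere is the number with eligible HGG stated.

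**Step 3: Part A patients added on top of the 10, common rate.** P = 1 − (1 − p)^(10 + k).

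| k | n | p = 5% | p = 20% |
|---|---|---|---|
| 0 | 10 | 40.1% | 89.3% |
| 2 | 12 | 46.0% | 93.1% |
| 4 | 14 | 51.2% | 95.6% |
| 10 | 20 | 64.2% | 98.8% |

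**Step 4: added on top, different rates.** If the RP2D has a true rate of 5% and the earlier regimens 20% (both assumed), P = 1 − 0.95^10 × 0.80^k. This gives 61.7% (k=2), 69.3% (k=3) and 80.4% (k=5), against 40.1% with RP2D patients only. In the extreme case of no activity at the RP2D, k=3 and an earlier rate of 20%, P = 1 − 0.80^3 = 48.8%, all of it from Part A.

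**Step 5: Part A patients inside the 10.** If they fill k places, the probability of a response among the remaining RP2D patients at a 20% rate is 1 − 0.80^(10 − k): 83.2% (k=2) and 67.2% (k=5), against 89.3%.

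**Step 6: what these figures are not.** Section 11.1 counts a minor response (MR) as a response, but a lone MR does not meet the rule. With 10 patients, P(pass) therefore depends on the mix of responses. If all are PR or CR it equals the stated figure. If all are MR it is 1 − (1 − p)^10 − 10p(1 − p)^9.
- p = 0.05: 1 − 0.5987 − 0.3151 = 8.6%
- p = 0.20: 1 − 0.1074 − 0.2684 = 62.4%

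So P(pass) lies between 8.6% and 40.1% at a 5% rate, and between 62.4% and 89.3% at 20%. Steps 1 and 3 to 5 give the chance of seeing at least one response, which is also what the plan reports.

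**The case against.** Several points on the other side have weight.

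- **The rule is about the drug.** Section 11.1 asks whether the agent merits further evaluation in this disease and names no regimen. A reader might infer that one twice-weekly response would formally declare weekly selinexor at the RP2D worth pursuing. The text does not go that far; the link to the RP2D comes from how Part B is defined. What stands is that the cohort meant to supply the evidence is an RP2D cohort and the stated probabilities assume one rate.
- **Earlier regimens were not dropped for inactivity.** Section 2.6 gives toxicity and tolerability as the reasons and cites equivalent efficacy of once- and twice-weekly dosing in adults. Section 2.8 argues that exposure at 35 mg/m2 in children at least matches that of the adult 80 mg flat dose. On those premises, pooling patients treated at 35 mg/m2 is defensible. The exposure objection applies only to 20 mg/m2.
- **Foreknowledge is partial.** It is tempting to say that all Part A outcomes will be known before Part B opens. Section 11.1 lets Part B open alongside the pharmacokinetic expansion, so some pooled patients could be enrolled at the same time.
- **Placement of the sentence.** It follows the DLT closure rule, so its target could be questioned. The reference to response evaluability and the link back from Section 11.2.3 point to the activity rule.
- **Stakes and size.** The aim is secondary, Section 11.5 calls these analyses exploratory, and k may be small. If k is zero, the numbers do not change.

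These points lower the severity. None of them supplies the missing dose and schedule limit or the missing denominator.

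**Conclusion.** The point holds as a gap in definition. Sections 11.1 and 11.2.3 admit Part A patients to the Part B activity rule without regard to dose or schedule and leave open whether they count within the 10. The stated 89.3% and 40.1% are arithmetically right but describe 10 patients at a single rate, which need not be the group the rule is applied to. If patients are added at a common 5% rate, the probability of at least one response rises from 40.1% to 46.0% (k=2), 51.2% (k=4) or 64.2% (k=10). If they take places inside the 10, the chance of a response among RP2D patients at a 20% rate falls instead. The size rests on k and on the earlier regimens' response rates, neither of which the documents give.

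A reader might go further and take 40.1% as the chance of passing, or see a threat to the trial's main conclusions. The documents support neither: 40.1% is the chance of at least one response, MR included, and dose finding and the other primary aims do not use this rule. Severity: should be fixed.

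**What to change.** In Sections 11.1 and 11.2.3:

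1. Limit the Part A patients who enter the activity rule to those treated at the declared RP2D on the Part B schedule.
2. State that the rule is applied to a fixed 10 evaluable patients and that pooled Part A patients count within that 10. This also removes the mixed use of enrolled and evaluable as the denominator.
3. Report responses in HGG patients treated at other doses or schedules separately and descriptively.

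The stated 89.3% and 40.1% then apply unchanged as probabilities of at least one response.

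**Cost.** A few sentences in an amendment, with no change to treatment or assessments. HGG patients from earlier regimens no longer inform the rule. Counting pooled patients within the 10 reduces new Part B accrual and may bring forward the closure of Part C, which Section 11.1 ties to Part B being fully accrued; the amendment should say how that closure is triggered. Some outcomes in RP2D patients from Part A may still be known when Part B opens, and the change does not remove that.

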**Amendment #4:**

Week	Day	Agent: Selinexor
1	1	X
2	8	X
3	15	X
4	22	X

With Amendment #4, patients will receive selinexor once weekly, on Days 1, 8, 15, and 22 of a 28-day cycle. The drug will be administered in tablet form with food. Patients may continue for a maximum of 24 cycles. Refer to [Section 7.3](#) for recommended supportive care guidelines.

Drug doses should be adjusted based on the BSA calculated from height and weight measured within 7 days prior to the beginning of each cycle (See [Appendix VI](#)). If a dose is vomited within 30 minutes of administration and there is visible evidence of the tablet, the dose should be repeated. If the tablet is not visible, or the dose is vomited later than 30 minutes after administration, the dose should not be repeated. The patient/caregiver should make a note of the vomited dose and whether there is visible evidence of the tablet on the pill diary and proceed with the next dose at the next scheduled time of administration.

Selinexor is supplied by Karyopharm Therapeutics. **Do not use commercial supply.**

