5.3.3 Part C: Surgical HGG Expansion Cohort

Patients with HGG requiring resection (Part C) will be treated at the recommended phase 2 dose (RP2D) determined from the phase 1 component (Part A) of this trial for 2 doses prior to undergoing scheduled resection of their tumors (*i.e.* Surgical resection should occur after dose on Day 8 but before dose on Day 15 of Cycle 1). After recovery from surgery with wound healed (minimum 3 weeks) and meeting criteria in [Section 5.2](#), patients can resume selinexor at the same dose and schedule and continue therapy to complete Cycle 1 and continue with Cycle 2. Patients who fail to recover from surgery within 6 weeks will be removed from protocol therapy.

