#### 7.6 **Part C (HGG Surgical Expansion Cohort)**

For HGG patients who temporarily discontinue protocol therapy to undergo scheduled tumor resection, therapy may not be restarted until wound healed (minimum 3 weeks) and until recovery to eligibility requirements ([Section 4.0](#)). Although patients will not be taking selinexor during the recovery period, platelets should be monitored as part of the twice weekly CBCs required during Cycle 1 as per [Section 8.1](#), and platelets should be maintained at a safe level to prevent post-operative bleeding as per institutional standards. Failure to adequately recover from surgery within 6 weeks after surgery will require removal from protocol therapy.

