**APPENDIX III: PHARMACOKINETIC STUDY FORM**

COG Pt ID # \_\_\_\_\_ ACC # \_\_\_\_\_

Please do not write patient names on this form or on samples.

Cycle 1, Day 1 Date: \_\_\_/\_\_\_/\_\_\_/\_\_\_/\_\_\_ Dose Level: \_\_\_\_\_mg/m^2 Dose Administered: \_\_\_\_\_mg

Plasma samples (1 mL) will be collected for pharmacokinetic studies at the time points listed in the table below. Record the exact date and time each sample is drawn and the time of the selinexor administration. In the event the dose is vomited within 30 minutes after administration on Cycle 1, Day 1 **and** there is no visible evidence of the tablet, the PK samples #2-9 should be collected after the second dose on Cycle 1, Day 3.

Blood Sample No.	Barcode # (from Sample Label)	Time Point	Scheduled Sample Collection Time	Scheduled Selinexor Time Point	Actual Date Sample Collected or Dose Given	Actual Time Sample Collected or Dose Given (24-hr clock)
1		Cycle 1, Day 1	Prior to Dose on Cycle 1, Day 1		___/___/___	__:__:__
				Cycle 1, Day 1	___/___/___	__:__:__
2		Cycle 1, Day 1	30 min. after Day 1 dose		___/___/___	__:__:__
3		Cycle 1, Day 1	1 hour after Day 1 dose		___/___/___	__:__:__
4		Cycle 1, Day 1	2 hour after Day 1 dose		___/___/___	__:__:__
5		Cycle 1, Day 1	3 hour after Day 1 dose		___/___/___	__:__:__
6		Cycle 1, Day 1	4 hour after Day 1 dose		___/___/___	__:__:__
7		Cycle 1, Day 1	6 hour after Day 1 dose		___/___/___	__:__:__
8		Cycle 1, Day 1	8 hour after Day 1 dose		___/___/___	__:__:__
9		Cycle 1, Day 2	24 (± 2) hr after Day 1 dose		___/___/___	__:__:__

Part C: An additional PK sample will be collected after 2 doses prior to Tumor Resection. Surgical resection should occur after dose on Day 8 but before dose on Day 15 of Cycle 1.

Blood Sample No.	Barcode # (from Sample Label)	Time Point	Scheduled Sample Collection Time	Scheduled Tumor Resection Date	Actual Date Sample Collected or Date of Resection	Actual Time Sample Collected or Dose Given (24-hr clock)
10		After 2 doses	Prior to Tumor Resection		___/___/___	__:__:__
				___/___/___	___/___/___	__:__:__

Refer to [Section 8.3](#) processing and shipping details. One copy of this Pharmacokinetic Study Form should be uploaded into RAVE.

If this form will be used as a source document, the site personnel who collected the samples must sign and date this form below:

Signature: \_\_\_\_\_

Date: \_\_\_\_\_

THIS PROTOCOL IS FOR RESEARCH PURPOSES ONLY, SEE PAGE 1 FOR USAGE POLICY

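### Part C contradicts itself twice: Section 11.1 allows up to four pre-operative doses where the operative sections give two, and footnote 8 of Section 8.1 can be read to suspend the post-operative CBCs that Section 7.6 relies on

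*Combined protocol and SAP*

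**What the plan says.** **Pre-operative doses.** The Part C description in Section 11.1 reads: "These patients will be allowed to receive up to four doses of selinexor prior to resection". Three other places differ. Eligibility (Section 4.1.3.3) admits patients who "are medically stable to receive 2 doses of selinexor (8-10 days of treatment) before undergoing surgery". The treatment section (5.3.3) gives the recommended dose "for 2 doses prior to undergoing scheduled resection of their tumors". The pharmacokinetic form (Appendix III) takes the extra Part C sample after two doses and states: "Surgical resection should occur after dose on Day 8 but before dose on Day 15 of Cycle 1". Section 5.3.3 sets the same window. Under Amendment #4 (Section 5.1), "patients will receive selinexor once weekly, on Days 1, 8, 15, and 22 of a 28-day cycle".

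**Post-operative CBCs.** Section 7.6 is explicit that it concerns time off drug ("Although patients will not be taking selinexor during the recovery period"). For that time its instruction is that "platelets should be monitored as part of the twice weekly CBCs required during Cycle 1", with a cross-reference to Section 8.1. It adds that "platelets should be maintained at a safe level to prevent post-operative bleeding as per institutional standards". In the Section 8.1 table the Cycle 1 CBC row is twice weekly, every 3 to 4 days. The heading of that Cycle 1 column carries footnote 8. The footnote confines required Part C observations to time on protocol treatment and lets labs described as weekly, together with observations, be deferred through a surgery window until therapy restarts. The window is not defined.

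**The concern.** Both conflicts are in current operative text, not in a log of changes.

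The first leaves two different limits on drug exposure before brain surgery. Section 4.1.3.3 asks the treating physicians to judge whether the child can safely wait for two doses. Using the Section 11.1 allowance in full would put surgery after the period they were asked to judge, and would also move the tumor-tissue sample that is a stated purpose of the cohort.

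The second leaves Section 7.6 leaning on a requirement that Section 8.1 may have switched off for the same period. The drug lowers platelets (Section 2.7) and the setting is recovery from neurosurgery. There is also a counting issue. Section 11.1 closes Part C if more than one-third of patients have DLT. Section 5.5.2 counts Grade 4 thrombocytopenia, and Grade 3 lasting at least 7 days, as DLT. If CBCs are held, an attributable event that resolves before restart is counted only if a locally ordered CBC happens to catch it. The explicit rule that toxicity monitoring must be done for a patient to be evaluable for DLT (Section 11.2.1) is written for Part A, so it does not fill the gap in Part C.

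**Working it through.** **Doses that fit before the Day 15 dose** (dose days from Section 5.1; window from 5.3.3 and Appendix III)

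| Schedule | Dose days before Day 15 | Number | Day of fourth dose |
|---|---|---|---|
| Weekly (Amendment #4, current) | 1, 8 | 2 | 22 |
| Twice weekly (superseded) | 1, 3, 8, 10 | 4 | 10 |

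The figure of four in Section 11.1 is reproduced exactly on the superseded schedule and cannot be reached on the current one. Even a third dose, on Day 15, falls outside the window. That the sentence was carried over from the twice-weekly plan is an inference, but it fits.

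**Cumulative pre-operative dose** (levels from Section 5.3.1, Amendment #4)

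| Level (mg/m²) | Two doses (mg/m²) | Four doses (mg/m²) |
|---|---|---|
| 35 | 2 × 35 = 70 | 4 × 35 = 140 |
| 45 | 2 × 45 = 90 | 4 × 45 = 180 |
| 55 | 2 × 55 = 110 | 4 × 55 = 220 |

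**CBCs during recovery** (minimum 3 weeks, removal from therapy if not recovered by 6 weeks: Sections 5.3.3 and 7.6)

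- Under Section 7.6, two per week: 2 × 3 = 6 to 2 × 6 = 12.
- By the table's 3- to 4-day spacing: 21/4 = 5.25 to 42/3 = 14, so about 5 to 14.
- Under the broad reading of footnote 8: none during the hold. The one remaining check is the restart requirement, which comes from Sections 5.2 and 5.3.3, not from the footnote.

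**Two readings of footnote 8**

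- *Narrow.* The second clause speaks of weekly labs. The table separates rows marked weekly from the CBC row marked twice weekly. On this reading the CBCs continue and Section 7.6 stands.
- *Broad.* The lead clause limits all Part C observations to time on protocol treatment, and the footnote is attached to the whole Cycle 1 column. On this reading the CBCs may be held, and Section 7.6 points to something that is not required.

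The text supports either reading.

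**Sensitivity of the closure rule to one missed event** (more than one-third; up to 10 evaluable patients)

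- Six patients: 2/6 = 33.3%, not above one-third, so accrual continues; 3/6 = 50%, closes.
- Ten patients: 3/10 = 30%, continues; 4/10 = 40%, would meet the closure criterion.

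Near the boundary one uncounted DLT changes the decision. This shows how the rule responds; it does not say how likely such an event is.

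**The case against.** **On the dose count.** The two-dose intent is clear from three places, two of which fix the surgical window. Section 11.1 sets a ceiling, which two doses satisfy. A site that gave more would breach Section 5.3.3, and no analysis or sample size uses the number. All of this stands, and it makes the point a correction of stale text. A reader might infer that Part C patients are meant to receive, or are likely to receive, four doses. The documents do not support that.

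**On the CBCs.** Section 7.6 is the specific provision for this cohort and period, so it can fairly be read to prevail over a general footnote. Platelets cannot be kept at a safe level without being measured. Section 6.1.2 requires counts every 2 to 3 days once Grade 4 or dose-limiting Grade 3 thrombocytopenia is found. Section 10.1 continues the required observations for patients removed from therapy in Cycle 1. These points narrow the gap but do not close it. Section 6.1.2 starts only after an event is detected. Section 10.1 covers patients removed from therapy, not those interrupted for surgery. Institutional standards are not a protocol schedule.

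**On the missed DLT.** It needs a site to take the broad reading, a qualifying event after two weekly doses, recovery before restart, and no clinical CBC in the weeks after surgery. The documents give no probability for that chain. The adult weekly glioblastoma arm lists no Grade 3 or 4 thrombocytopenia among 30 patients (Section 2.4), against 12% for solid tumors overall (Section 2.7). This stands: the effect is possible under-counting, not demonstrated under-counting.

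**Conclusion.** Two internal contradictions in operative Part C text should be corrected.

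The first is certain. Section 11.1 allows up to four pre-operative doses, while three other places give two, and on the weekly schedule only two fit the window. Followed literally, it would double pre-operative exposure and move surgery to Day 22 or later.

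The second is an ambiguity with two reasonable readings, worth about 6 to 12 protocol-required CBCs per patient over recovery. Its effect is that required post-operative platelet monitoring may differ between sites, and that hematologic DLT may be under-ascertained for the Part C closure rule. This rests on some sites adopting the broad reading.

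Stronger conclusions are not supported. A reader might infer that children go without platelet checks after neurosurgery. Section 7.6 still calls for safe platelet levels under institutional standards, and restart needs the laboratory criteria to be met again. A reader might also infer from Section 2.7 that the platelet nadir falls inside the recovery period. Those adult data come from 7 to 8 doses per cycle on a twice-weekly schedule, and nothing is given on timing or depth after two weekly doses. The primary aims, the sample size and the Part B activity rule do not depend on either point.

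**What to change.** 1. In Section 11.1 (Part C), replace the four-dose allowance with two doses of selinexor, on Days 1 and 8, with resection before the Day 15 dose. This matches Sections 4.1.3.3 and 5.3.3 and Appendix III.
2. In footnote 8 of Section 8.1, state that CBC with platelets is excepted from the hold and continues twice weekly, per Section 7.6, until protocol therapy resumes.

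The cost is two one-line wording changes. No procedure is added beyond the CBCs that Section 7.6 already assumes; only a site that had taken the broad reading of footnote 8 would draw more blood than it now does.
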